### 2.3.6. Medication Compliance

Patients will record the doses of urea they consume each day during treatment period in a study diary which will be reviewed during study visits.

We will be assessing patient compliance with urea as described above so patients will not be withdrawn due to non-compliance with the study drug. If patients are noncompliant with serum sodium checks such that the PIs believe the patient should not continue to take urea, we will formally discuss the case with the study team and if it is agreed by all members of the study team that the patient be withdrawn, they will be asked to stop study drug, return remaining doses, and will be formally withdrawn from the study

Subjects withdrawn from the study will be replaced. We will continue recruitment until the target number of patients are enrolled.

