## 2.3 STUDY DRUG

The drug to be administered is urea (brand name Ure-Na™). Urea is a medical food or dietary supplement considered by the FDA under the GRAS (Generally Regarded As Safe) category. Patients will be instructed to start urea at a dose of 15 g once daily. Dose titration then will occur based on the absolute increase in PNa on days 7 and 14 as follows:

- Day 7: If PNa increases ≥3 mmol/L from baseline, then continue same urea dose. If PNa increases <3 mmol/L from baseline, then increase urea to next dose.
- Day 14: If PNa increases ≥ 6 mmol/L from baseline, or PNa increases <6 mmol/L from baseline and PNa ≥135 mmol/ L, then continue same urea dose. If PNa increases <6 mmol/L from baseline and PNa <135 mmo/L, then increase urea to next dose.

The dosing scheme for urea will involve increasing when appropriate, from the starting dose of 15 g/day, to 30 g/day in 2 divided doses, and subsequently, when appropriate, from 30 g/day to 60 g/day (in 2 divided doses). The maximal dose of urea administered will be 60 g/day. The route of administration will be oral and the total duration of administration will be  $42 \pm 3$  days.

Oral urea use is occasionally associated with the onset of nausea, vomiting, diarrhea and headaches. If these symptoms appear then they will be initially managed by asking patients to monitor their symptoms and report to the research coordinator if symptoms persist after

24h. If symptoms persist, urea dose will be reduced by 50%. If symptoms persist 72h after reducing the dose of urea, urea will be discontinued.

Subjects will be seen at the UPMC kidney clinic immediately after the completion of their participation in the study for consideration of continuation of urea therapy.

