### 2.3.1. Study Drug Preparation and Dispensing

The study drug will be donated by Nephcentric, the manufacturer of Ure-Na™. Ure-Na™ is formulated as a powder packaged in a 21-g pouch or sachet. Each pouch of Ure-Na™ contains 15 g of pharmaceutical grade urea and 6 g of other ingredients including natural flavors, citric acid, maltodextrin, calcium silicate, and sucralose. The powder is then mixed with 3 to 4 oz. of water or juice for oral consumption. No on-site preparation of the study drug will be performed. Patients will be given 6 boxes of Ure-Na™ each containing eight pouches (total of 48 pouches) and instructed to take the study drug at home as indicated. Some more pouches of Ure-Na™ will be given at day 14 as necessary to complete their participation in the study.

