## 4. IRB APPROVAL AND FDA AMENDMENTS

The Investigator will obtain, from the University of Pittsburgh Institutional Review Board (IRB), prospective approval of the clinical protocol and corresponding informed consent form(s); modifications to the clinical protocol and corresponding informed consent forms, and advertisements (i.e., directed at potential research subjects) for study recruitment.

The only circumstance in which a deviation from the current IRB-approved clinical protocol/consent form(s) may be initiated in the absence of prospective IRB approval is to eliminate an apparent immediate hazard to the research subject(s). In such circumstances, the Investigator will promptly notify the University of Pittsburgh IRB of the deviation. The Investigator should also notify the sponsor of this event.

The University of Pittsburgh IRB operates in compliance with FDA regulations at 21 CFR Parts 50 and 21 CFR 56, and in conformance with applicable International Conference on Harmonization (ICH) Guidelines on Good Clinical Practice (CGP).

In the event that the University of Pittsburgh IRB requires, as a condition of approval, substantial changes to a clinical protocol submitted under an FDA-accepted IND application, or in the event of the Investigator's decision to modify the previously accepted clinical protocol:

• for a Phase 1 clinical study: The Sponsor will submit (i.e., in advance of implementing the change) a Protocol Amendment to the IND describing any change to the Phase 1

clinical protocol that significantly affects the safety of the subjects. For changes that do not affect critical safety assessments, the revisions to the clinical protocol will be addressed in the Annual Report to the IND.

- for Phase 2 and 3 clinical studies: The Sponsor will submit (i.e., in advance of implementing the change) a Protocol Amendment to the IND describing any change to a Phase 2 or Phase 3 protocol that significantly affects the safety of subjects, the scope of the investigation, or the scientific quality of the study. Examples of Phase 2 and 3 clinical protocol changes requiring the submission of a Protocol Amendment include:
  - Any increase in drug dosage or duration of exposure of individual subjects to the investigational drug beyond that described in the current protocol, or any significant increase in the number of subjects under study.

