## 9.4 FREQUENCY OF MONITORING

The Investigator will review subject safety data as it is generated. The Investigator, subinvestigators, and the research staff will meet on a 4-week interval to re-evaluate study goals, subject recruitment, data coding and retention, documentation and identification of adverse events, complaints and confidentiality of subjects. There will be an evaluation of the progress of the research study, including assessments of data quality, timelines, participant recruitment, accrual, and retention. The Investigator will also review the outcome and adverse event data to determine whether there is any change to the anticipated benefit-to-risk ratio of study participation and whether the study should continue as originally designed or should it be reevaluated and changed.

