## **10. WITHDRAWAL OF SUBJECTS AND STOPPING CRITERIA:**

Adverse Events: Oral urea use is occasionally associated with the onset of nausea, vomiting, diarrhea and headaches. If these symptoms appear then they will be initially managed by asking patients to monitor their symptoms and report to the research coordinator if symptoms persist after 24h. If symptoms persist, urea dose will be reduced by 50%. If symptoms persist 72h after reducing the dose of urea, urea will be discontinued. Participant will be asked to return remaining urea doses, and after consultation with all the members of the research team, participant will be formally withdrawn from the study. Data no longer will be collected from the withdrawn subject and subject will be referred to the UPMC kidney clinic for follow up. Subjects withdrawn from the study will be replaced using the regular procedures described for recruitment. We will continue recruitment until the target number of patients are enrolled.

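### Section 2.3.6 lets urea be stopped for missed sodium checks only once the whole study team agrees to withdrawal, although the PIs already judge that it should not continue (minor)

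*Combined protocol and SAP*

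**What the plan says.** Section 2.3.6 (Medication Compliance) first says that patients are not withdrawn for failing to take urea, because adherence is itself being measured. It then sets out a separate ground, for patients who are "noncompliant with serum sodium checks such that the PIs believe the patient should not continue to take urea". Their case goes to a formal team discussion under this rule: "if it is agreed by all members of the study team that the patient be withdrawn, they will be asked to stop study drug". They also return their remaining doses and are formally withdrawn.

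For persistent nausea, vomiting, diarrhea or headache, sections 2.3 and 10 give another sequence. The dose is halved, and then: "If symptoms persist 72h after reducing the dose of urea, urea will be discontinued". In section 10 the team enters after that step: "after consultation with all the members of the research team, participant will be formally withdrawn from the study". Section 10 adds, for this adverse-event route, "Data no longer will be collected from the withdrawn subject". It lists no other withdrawal criteria, so it does not point to the ground in section 2.3.6.

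On supply, section 2.3.1 gives each patient 48 pouches of 15 g at the start of urea. Further pouches "will be given at day 14 as necessary to complete their participation in the study".

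**The concern.** Section 2.3.6 applies only where the PIs have already concluded that a patient should not go on taking urea without sodium checks. That is a dosing judgement. The instruction that would act on it is tied to a different decision, whether the patient leaves the study, and that decision needs every team member's agreement. If one member disagrees, the section gives no instruction at all about the drug.

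Two things are at stake. One is safety: a patient may keep taking urea, unmonitored, against the PIs' own judgement. The other is follow-up: the only written route to stopping urea on this ground is also a route out of the study. If section 10's end to data collection were applied here as well (it is written for adverse events), stopping the drug would also end follow-up, in a pilot of 30 patients.

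**Working it through.** No figure in the plan bears on this point, so the check is a comparison of texts followed by a look at the dose and supply involved.

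**1. The two sequences side by side**

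| | Missed sodium checks (2.3.6) | Persistent symptoms (2.3 and 10) |
|---|---|---|
| Trigger | PIs believe urea should not continue | Symptoms persist 72 h after the dose is halved |
| Next step | Formal team discussion | Urea is discontinued |
| Condition for stopping urea | All members agree to withdrawal | None beyond the trigger |
| What the team settles | Withdrawal, and through it the drug | Formal withdrawal only |
| If the team does not agree | Not stated | Drug already stopped |

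The triggers differ. The comparison concerns only the order of the drug stop and the team decision.

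**2. Whether another section supplies a hold**

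- Sections 2.2 and 2.3 change the dose on a sodium result or on side effects. A missed check produces neither.
- Section 2.3.7 limits prescribing to listed PIs and co-investigators, but gives no stop step.
- Section 4 allows a departure without prior IRB approval only where the hazard to a subject appears immediate. A missed blood test may not qualify.
- Section 9.2 requires adverse events to be reported, and section 9.4 has the investigator review safety data as they arise. Both are general, and a patient who misses checks generates no sodium data.

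None of these is a hold for this case.

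**3. Dose when a scheduled check is missed** (titration rule, section 2.2)

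- Day 7 missed: no result, no increase, so 15 g/day.
- Day 7 attended and the dose raised, day 14 missed: 30 g/day.
- Day 14 attended and the dose raised from 15 to 30 g/day, with the recheck about 7 days later missed: 30 g/day.
- Day 14 attended and the dose raised to 60 g/day: this is the maximum dose, so no recheck is required before day 42, when urea ends anyway.

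The dose after a missed check before day 42 is therefore 15 or 30 g/day. Section 2.3.3 cites a guideline range of 0.25 to 0.5 g/kg/day, which for 60 kg is 0.25 × 60 = 15 to 0.5 × 60 = 30 g/day.

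**4. Whether withholding resupply would do the job**

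- At one pouch a day, 48 pouches last 48 days, beyond the longest urea period of 42 + 3 = 45 days.
- At two pouches a day from day 7: (48 − 7) / 2 = 20.5 days, so supply lasts to about day 27.
- At two pouches a day from day 14: (48 − 14) / 2 = 17 days, so supply lasts to day 31.

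Withholding resupply limits exposure at 30 g/day. It does nothing for a patient who missed the day 7 and day 14 checks and remains on 15 g/day. That patient needs an instruction to stop.

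**The case against.** The strongest reply is that little turns on this in practice. The text does not forbid a PI from asking a patient to pause urea, and the PIs control prescribing. Sections 2.5.4 and 6.1.1 rate the risk of osmotic demyelination as negligible at PNa ≥125 mmol/L without serious liver disease. The protocol also accepts long unmonitored stretches in compliant patients: someone whose dose is unchanged at day 14, or raised to 60 g/day then, has no scheduled check for 42 − 14 = 28 days. That comparison is inexact, because such a patient does have a day 14 result. Finally, section 10 also ends in withdrawal, so it is a precedent for stopping the drug first but not for keeping the patient enrolled with urea on hold.

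All of this stands, and it limits the size of the point. It does not supply the missing instruction.

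Three stronger readings are tempting, and the documents do not support them:

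- A reader might infer a delay of up to four weeks, because section 9.4 says that the investigators and "the research staff will meet on a 4-week interval". Section 2.3.6 does not refer to that meeting, and a discussion could be called the same day.
- A reader might suppose that the patient could be taking 60 g/day while the team decides. The titration schedule does not lead there after a missed check.
- A reader might suspect that members would hesitate over withdrawal for reasons unrelated to dosing. Nothing in the documents says so, and the replacement of withdrawn subjects lowers the recruitment cost of agreeing.

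**Conclusion.** The point holds as a minor one. Section 2.3.6 states an operative rule that puts the stop instruction last and makes it conditional on unanimous agreement about study membership, after the PIs have already judged against continuing. It gives no interim hold and no path for disagreement, and no other section fills the gap. Section 10 shows that the protocol already stops the drug first in a comparable situation.

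The expected safety gain from changing the order is small: at most 30 g/day is at stake when a scheduled check before day 42 is missed, and the protocol considers the main risk negligible. The dose limit assumes that the titration rule is followed as written. The documents give neither a rate of missed checks nor a time for the team discussion, so the number of patients affected and the length of any delay cannot be estimated.

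**What to change.** In section 2.3.6, state that:

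- the PI holds urea, and any resupply, as soon as the PI judges that it should not continue;
- only formal withdrawal awaits the team discussion;
- until that decision the patient stays enrolled, on scheduled follow-up, with urea recorded as held;
- urea restarts only when a sodium result is available and the PI agrees.

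In section 10, replace the statement that there are no other criteria with a cross-reference to section 2.3.6.

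Leave the adherence denominator as it is and report held days separately. Removing held days from the prescribed doses would alter a primary adherence endpoint and could raise measured adherence in the very patients who are not complying.

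The cost is wording in two sections and one short interim status to define. No visit, procedure or staff is added. The downside is that some patients will have interrupted dosing in the crossover analysis. Section 2.5.3 does not say how a day 42 value after an interruption is used, so a sentence there would be sensible.

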### 2.3.7. Medication Storage and Accountability

The UPMC Investigational Drug Services (IDS) will be utilized in this study. They are a separate pharmacy who only handles investigational drugs. Each drug is stored in a separately labeled bin in a temperature controlled environment. All files and drug are kept in a locked pharmacy and only IDS staff has access. Only PI's and Co-I's that we list on the order form are able to prescribe the investigational product.

IDS creates a study binder to maintain accountability. The IDS staff will log every time there is a dispense or they receive medication. The IDS staff will maintain patient accountability keeping a separate tab in the binder for each patient enrolled. The IDS staff will file all invoices for the investigational product.

At the end of the study, all the unused investigational product shall be transferred to the IDS accountability and destruction. The investigational product returns will be accounted for by both the study team and pharmacy. The study team will provide the first count followed by a second count performed by the IDS staff. The IDS staff will reconcile the count returned with the research coordinator and document in the accountability log. After reconciliation the investigational product will be immediately discarded into the appropriate waste stream containers.

#### 2.3.8 Concomitant Medications

During their participation in the study, subjects will not be allowed to take the following medications:

- Vasopressin antagonists: tolvaptan, conivaptan

- Thiazide and thiazide-like diuretics: hydrochlorothiazide, chlorothiazide, bendroflumethiazide, chlorthalidone, indapamide, metolazone
- Osmotic diuretics: mannitol
- Carbonic anhydrase inhibitors: acetazolamide, topiramate
- Desmopressin
- Demeclocycline

Subjects' medical history will be reviewed during every subject's study visit looking for changes in health status, hospitalizations, and new prescription drugs. In addition, subjects will be asked about the use of any new medication (prescription or non-prescription) during every study visit including the ones listed above.

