## 2. RESEARCH DESIGN AND METHODS

### 2.1 CLASSIFICATION AND METHODOLOGICAL DESIGNS

The proposed pilot study is designed as a prospective, cross-over trial. Over a 13.5-month period, we will recruit 30 outpatients with chronic non-severe hyponatremia (PNa 125 to 132 mmol/L) confirmed to be due to SIADH. Subjects will not be withdrawn from any known effective therapy for chronic hyponatremia for the purpose of participating in this study. Following enrollment, patients will be randomly assigned on 1:1 ratio to one of two sequence groups. Patients assigned to group "Urea ON, then Urea OFF" will receive oral urea for 42 ± 3 days (period 1), followed by a 10 ± 4-day period in which all patients will be off urea (washout period). Patients then will be off urea for 42 ± 3 days (period 2). Patients assigned to group "Urea OFF, then Urea ON" will be off urea therapy for 42 ± 3 days (period 1), and following a 10 ± 4-day washout period then they will initiate urea for 42 ± 3 days (period 2). Patients will have PNa assessed at baseline and on days 7 ± 2, 14 ± 2, and 42 ± 3 during periods 1 and 2 of the study and will undergo neurocognitive and postural control and stability testing on days 0 and 42 of each of the study periods. All patients will be advised to restrict their fluid intake to ≤1.2 liters during periods 1 and 2.

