#### Intervention (oral urea) and study period 1:

Patients randomized to study group "Urea ON, then Urea OFF" (N=15) will begin 42 ± 3 days of urea therapy, while those randomized to study group "Urea OFF, then Urea ON" (N=15) will not receive urea during this period. All patients will be asked to restrict their fluid intake to  $\leq$ 1.2 L/day during period 1. We will provide participants with a protocol for recording their daily fluid intake which includes carefully measuring all ingested fluids with a measuring cup and recording them on a study diary during the entire study period. We will use the new American formulation of oral urea (i.e., Ure-NaTM), which is packaged as a powder that is mixed with 4 oz. of water for oral consumption. Group "Urea ON, then Urea OFF" patients will be given 48 powder pouches of Ure-Na (15 g of urea per pouch) and will be instructed to start at a dose of 15 g once daily. Dose titration will be based on the absolute increase in PNa on days 7 ± 2 and 14 ± 2 as follows:

- Day 7: If PNa increases ≥3 mmol/L from baseline, then continue same urea dose. If PNa increases <3 mmol/L from baseline, then increase urea to next dose.
- Day 14: If PNa increases ≥ 6 mmol/L from baseline, or PNa increases <6 mmol/L from baseline and PNa ≥135 mmol/ L, then continue same urea dose. If PNa increases <6 mmol/L from baseline and PNa <135 mmo/L, then increase urea to next dose.

The dosing scheme for urea will involve increasing when appropriate, from the starting dose of 15 g/day, to 30 g/day in 2 divided doses, and subsequently, when appropriate, from 30 g/day to 60 g/day (in 2 divided doses). The maximal dose of urea administered will be 60 g/day. Patients will undergo a PNa check approximately  $7 \pm 2$  days after a urea dose adjustment to less than the maximal dose of urea allowed. Patients will record the doses of urea they consume each day during treatment period 1 in the study diary.

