#### Research activities

Screening visit

• Patient will come in person to the UPMC Kidney Clinic.

- For Nephrology inpatients who meet eligibility for the study and have not started urea in the hospital, we will obtain informed consent during their hospitalization and schedule them for a screening visit within approximately 5-7 days after discharge. For Nephrology inpatients who meet eligibility for the study including a nadir serum sodium of no less than 125 mmol/L and have already started urea in the hospital, we will obtain informed consent during hospitalization, discuss with the nephrologist and/or hospitalist, we will ask them if the patient can come off urea and if so, to discontinue urea. We will then schedule these patient for a screening visit within 5-7 days after discharge. Screening visit for subjects enrolled from inpatient will take place at UPMC Kidney Clinic.
- For Nephrology outpatients who meet eligibility for the study including a nadir serum sodium of no less than 125 mmol/L and are already on urea, we will obtain informed consent, discuss with the nephrologist, we will ask them if the patient can come off urea and if so, to discontinue urea. We will then schedule these patients for a screening visit within 5-7 days after urea discontinuation. Screening visit for subjects enrolled from the outpatient setting will take place at UPMC Kidney Clinic.
- The principal investigator will obtain informed consent from the patient to be enrolled in the study.
- Patient will undergo a physical examination by principal investigator which involves: assessment of patient's ability to walk normally without help, assessment of patient's cognition with the use of the Mini-Mental State Examination test, and assessment of volume status
- The research coordinator will draw approximately 14 mL of patient's blood and send the specimen promptly to the UPMC Presbyterian clinical laboratory for processing and analysis of the following: basic metabolic panel, plasma cortisol, thyroid stimulating hormone, and plasma osmolality..
- The research coordinator will ask the patient to provide a urine sample. The research coordinator will send the specimen promptly to the UPMC Presbyterian clinical laboratory for processing and analysis of the following: urine osmolality, urine sodium, and urine pregnancy test when indicated.

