#### 2.3.9 Rescue Medications

No rescue medications will be used during this study.

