# **3.3 EXCLUSION CRITERIA**

- a. Cirrhosis and/or end-stage liver disease
- b. Heart failure on diuretics and/or with recorded left ventricular ejection fraction <40%
- c. Chronic kidney disease with most recent estimated glomerular filtration rate < 45 ml/min/1.73m2
- d. Adrenal insufficiency
- e. Untreated hypothyroidism
- f. Urinary tract obstruction within the prior 2 months
- g. Uncontrolled hyperglycemia (most recent random plasma glucose ≥ 200 mg/dL)
- h. Ongoing drug treatment for hyponatremia with vaptans or combination of loop diuretics and salt tablets.
- i. Active malignancy (not on remission)
- j. Active infection
- k. Neurological disorders with impairment of ambulation and/or cognition
- I. End-stage lung disease with marked impairment in ambulatory capacity
- m. Chronic pain with impairment of ambulation and/or cognition
- n. Chronic nausea
- o. Hypersensitivity to urea
- p. Women who are pregnant, breast feeding, or of childbearing potential who are not using contraception
- q. Patient is unable to consent for himself/herself

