For all patients meeting these inclusion and exclusion criteria, we will contact their primary care provider (PCP) to discuss the study and their patients' potential eligibility. We will ask PCPs for permission to mail a letter to their patient on the PCP's behalf that introduces the study and describes how the patient can contact our study team if they are interested in participating. The letter will also state that if patients do not contact our team within 2 weeks, we will call them to inquire about their interest in participating in the study. This process of identifying and contacting potential study subjects has been deemed acceptable by the UPMC Institutional Review Board.

For Nephrology outpatients and inpatients, if the patient is not known to a study team clinician, the study team will request a clinician known to the subject ask the subject if a research team member may approach. Upon confirmation from the clinician that the subject is interested, the study team will approach.

Third stage: For patients who are interested in potentially participating, we will proceed with the third step. This will involve an in-person visit to obtain written informed consent from the patient to perform a physical examination and laboratory testing to confirm the presence of hyponatremia and to establish the etiology as SIADH. This informed consent will also cover patient participation in the study (patients who fail this screening testing will have their consent to participate withdrawn).

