## **6.2 ALTERNATIVE TREATMENTS**

Alternative treatments include fluid restriction alone, loop diuretics with salt tablets, and tolvaptan.

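### The entry exclusions and the on-study prohibited list do not match: loop diuretic plus salt tablets is absent from Section 2.3.8, and five classes barred there are named in no entry criterion

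*Combined protocol and SAP*

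**What the plan says.** Section 2.3.8 (Concomitant Medications) states: "During their participation in the study, subjects will not be allowed to take the following medications". Six classes follow: vasopressin antagonists, thiazide-type diuretics, osmotic diuretics (mannitol), carbonic anhydrase inhibitors, desmopressin and demeclocycline. It also says that participants will be asked about new medication at every visit.

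Exclusion h in Section 3.3 reads: "Ongoing drug treatment for hyponatremia with vaptans or combination of loop diuretics and salt tablets". The synopsis and the second recruitment stage in Section 5.1 carry the same exclusion. The only other entry criterion that mentions diuretics is exclusion b, which applies only to patients with heart failure.

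Section 6.2 states: "Alternative treatments include fluid restriction alone, loop diuretics with salt tablets, and tolvaptan". Section 2.3.9 states: "No rescue medications will be used during this study"; it names no drug.

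On timing, the third recruitment stage in Section 5.1 says: "This will involve an in-person visit to obtain written informed consent from the patient to perform a physical examination and laboratory testing". The screening-visit list in Section 2.2 likewise has "The principal investigator will obtain informed consent from the patient to be enrolled in the study" at the visit where the blood and urine samples are taken. Section 2.1 adds: "Subjects will not be withdrawn from any known effective therapy for chronic hyponatremia for the purpose of participating in this study".

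**The concern.** There are two gaps, running in opposite directions.

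First, the protocol treats loop diuretic plus salt tablets as a hyponatremia treatment that disqualifies at entry, and Section 1.3 says it raised plasma sodium (PNa) in small case series. Yet starting it during either period does not breach Section 2.3.8. PNa is a primary endpoint, the study is unblinded (Section 2.3.5), and OFF periods rest on fluid restriction alone for about 42 days. Section 1.3 estimates that as many as 70% of SIADH patients do not respond to fluid restriction alone. An outside clinician might therefore add the combination more often in OFF than in ON periods, which would shrink the ON-OFF difference.

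Second, five classes matter enough to be barred on study, but nothing says what to do with a candidate already taking one: exclude, stop, or stop how long before testing. If stopping the drug changes PNa, some patients could be classified as SIADH on values measured under a drug they then have to give up.

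**Working it through.** **The two lists side by side**

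| Treatment | Named at entry (3.3) | Barred on study (2.3.8) |
|---|---|---|
| Vaptans | Yes (h) | Yes |
| Loop diuretic plus salt tablets | Yes (h) | No |
| Thiazides | No; diuretic users with heart failure caught by b | Yes |
| Mannitol | No; same qualification | Yes |
| Carbonic anhydrase inhibitors | No | Yes |
| Desmopressin | No | Yes |
| Demeclocycline | No | Yes |

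The overlap is one treatment. One is on the entry list only, and five are on the on-study list only. None of the six Section 2.3.8 classes has a stated drug-free interval before screening or baseline.

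Of the three alternatives in Section 6.2, fluid restriction is advised for everyone and tolvaptan is on the Section 2.3.8 list. Only loop diuretic plus salt is left unaddressed there.

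**Timing for a current user of one of the five classes.** Suppose the bar starts at consent. On the standard route, consent and the screening tests fall at the same visit, so the SIADH tests can be drawn 0 days off the drug. For prior urea, the protocol does write a stop before screening, with the physician's agreement. The 5-7 days there is the time by which the visit should happen, not a minimum interval. For these five classes no stop step is written.

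**Size of the first gap.** Take the crossover estimate as ½[mean of (P1 − P2) in ON-first + mean of (P2 − P1) in OFF-first], with 15 patients per sequence and complete data. One extra OFF-period user who gains r mmol/L lowers one sequence mean by r/15, and so the estimate by r/30. For d net extra OFF users the shift is d × r/30:

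- d = 1, r = 1: 0.033 mmol/L
- d = 1, r = 3 (assumed): 0.10 mmol/L
- d = 3, r = 3 (assumed): 0.30 mmol/L

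For scale only, the tolvaptan-placebo gaps in Section 1.3 are 6.2 − 1.7 = 4.5 and 6.2 − 1.8 = 4.4 mmol/L. A shift of 0.10 is 2.2% to 2.3% of these.

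**Size of the second gap.** Assume that k of 30 patients stop a drug near day 0 and that each shifts by s = 3 mmol/L in period 1. The size, the direction and the timing are all assumptions. Drug use at entry precedes randomisation, so the split of the k patients between sequences is random. The induced error has mean 0 and SD (s/15) × √[k × 0.25 × (30 − k)/29]:

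- k = 1: 0.100 mmol/L
- k = 2: 0.139 mmol/L
- k = 3: 0.167 mmol/L

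For comparison, assume a change SD of 4.0 (the tolvaptan trials in Section 1.3 give 3.6 to 4.1) and a between-period correlation ρ of 0 to 0.5. The standard error of the contrast is ½√[2 × 2 × 16 × (1 − ρ)/15], which is 1.03 at ρ = 0 and 0.73 at ρ = 0.5. Adding 0.167 in quadrature raises it by about 1.3% and 2.6% respectively.

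**Titration.** The day-7 rule in Section 2.2 is: "If PNa increases ≥3 mmol/L from baseline, then continue same urea dose". A rise of 3 mmol/L from any cause meets it. The day-14 continue rule is met by a rise of min(6, 135 − baseline): 6 for baselines of 125-129, 5 for 130, 4 for 131 and 3 for 132. A drug-withdrawal rise could meet these thresholds only if the drug were stopped near day 0. It would matter mainly in ON-first patients. OFF-first patients start urea about 42 + 10 = 52 days after day 0 (39 + 6 = 45 to 45 + 14 = 59), from a re-measured baseline.

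**The case against.** The strongest case against is that this is editorial. Records are reviewed and the primary care provider is contacted before approach (Section 5.1). The investigator decides eligibility from the examination and laboratory results, and medications are recorded as study data (Section 7.1). A patient who must take a Section 2.3.8 drug cannot comply with participation, so the list works as an implicit bar. Section 2.3.9 rules out rescue medication. The trial is a 30-patient pilot that Section 2.5.3 describes as not powered to establish efficacy.

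Most of this limits the size of the point without removing it. An implicit bar does not say whether to exclude or stop, or how long before the tests. Section 2.3.9 reaches use by the study team but does not clearly reach an outside prescription. Section 2.1 covers known effective hyponatremia therapy, not drugs taken for other reasons.

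A reader might infer more than the documents support, in three ways:

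- **That stopping one of the five classes raises PNa.** No section says so. The Section 2.3.8 list does not run in one direction, since it also bars vaptans, which raise PNa.
- **That such a shift distorts titration or the day-42-versus-baseline hypothesis (Section 1.2, c).** Both use the day-0 baseline, which falls some time after screening. If the drug is stopped at consent, part or all of any shift may be over by then.
- **That the treatment estimate is biased by the second gap.** Section 2.5.3 plans a mixed model of period changes, not a separate pre-post test, and drug use at entry is balanced between sequences in expectation.

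**Conclusion.** The mismatch is real and can be checked from the text: two explicit rules disagree, which is more than missing detail. Its severity is minor.

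The first gap can pull the ON-OFF PNa difference towards no effect, by gain/30 per net extra OFF-period user. The documents give neither uptake nor effect size. The evidence that the combination raises PNa is small case series, and Section 1.3 says its components lack trial evidence. The shift is probably small unless use is common.

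The second gap can blur who counts as having SIADH and can add noise: an SD of about 0.10 to 0.17 mmol/L if one to three patients each shift by an assumed 3 mmol/L. It does not bias the randomised contrast in expectation. Effects on titration or on the change from baseline arise only if the drug is stopped near day 0.

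**What to change.** In Section 2.3.8, add loop diuretic plus salt tablets given as treatment for hyponatremia, barred in both periods.

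In Section 3.3, exclude current use of the five classes unless the drug is stopped, with the treating physician's agreement, before the screening laboratory tests. The investigators should set the minimum interval and state it in the protocol. Repeat the change in the synopsis and in the second recruitment stage of Section 5.1.

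Keep all PNa values in the main analysis, and record starts and stops of these drugs in the same way in ON and OFF periods. The existing visit question covers new medication only, so recording stops is a small addition.

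The cost is two list edits, one extra item at visits, and a few candidates screened out or delayed. That last cost counts a little, because recruitment feasibility is a primary aim.
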